#### **9.1.5. Adverse Events Leading to Treatment Discontinuation and/ or Study Discontinuation**

Below summary tables will be provided by KY1005 treatment regimen and in the Placebo group using count and percentages of patients:

- Number (%) of Patients with TEAEs leading to Treatment Discontinuation by SOC and PT from Baseline (Week 0) up to Week 24
- Number (%) of Patients with TEAEs leading to Treatment Discontinuation by SOC and PT from Week 24 up to Week 68
- Number (%) of Patients with TEAEs leading to Treatment Discontinuation by SOC and PT from Baseline (Week 0) to Week 68 based
- Number (%) of Patients with TEAEs leading to Study Discontinuation by SOC and PT from Baseline (Week 0) up to Week 24
- Number (%) of Patients with TEAEs leading to Study Discontinuation by SOC and PT from Week 24 up to Week 68
- Number (%) of Patients with TEAEs leading to Study Discontinuation by SOC and PT from Baseline (Week 0) to Week 68

All AEs leading to study drug discontinuation and study discontinuation will be listed by patients.

#### 9.1.6. AE leading to Death

Below summary tables will be provided by KY1005 treatment regimen and in the Placebo group using count and percentages of patients:

- Number (%) of Patients with TEAEs leading to Death by SOC and PT from Baseline (Week 0) up to Week 24
- Number (%) of Patients with TEAEs leading to Death by SOC and PT from Week 24 up to Week 68
- Number (%) of Patients with TEAEs leading to Death by SOC and PT from Baseline (Week 0) to Week 68
- Number (%) of Patients with Post-Study Adverse Events leading to Death by SOC and PT AEs leading to death will be listed by patients.

#### 9.1.7. Adverse Event of Special Interest (AESI)

Below summary tables will be provided by KY1005 treatment regimen and in the Placebo group using count and percentages of patients:

- Number (%) of Patients with AESI by AESI category and PT from Baseline (Week 0) up to Week 24
- Number (%) of Patients with AESI by AESI category and PT from Week 24 up to Week 68
- Number (%) of Patients with AESI by AESI category and PT from Baseline (Week 0) up to Week 68
- Post-treatment AESI by AESI category and PT
- Number (%) of Patients with AESI by AESI category, PT and Severity from Baseline (Week 0) up to Week 24
- Number (%) of Patients with AESI by AESI category, PT and Severity from Week 24 up to Week 68
- Number (%) of Patients with AESI by AESI category, PT and Severity from Baseline (Week 0) up to Week 68

The safety follow-up period following early discontinuation will be considered for the period when the discontinuation occurred in terms of identifying AEs that started in it.

The following AEs are considered as AESIs:

- Systemic or localised allergic reactions that require immediate treatment
- Severe injection site reactions that last longer than 24 hours.
- Any severe or opportunistic viral, bacterial or fungal infection and/or any uncommon, unanticipated or persistent infection (viral, parasitic, bacterial, or fungal).
- Any malignancy.
- Increase in alanine transaminase (ALT)  $>3 \times$  upper limit of normal (ULN); see the “Increase in ALT” flow chart in Section 17.12 (Appendix 12) of the protocol.

The special situations of:

- Symptomatic overdose (serious or non-serious) with IMP (overdose is defined as any administration that is twice or more than the intended dose administered in less than 3 weeks [21 days]) and symptomatic is defined as the event reported by the patient and/or the investigator.
- Pregnancy - discussed separately in Section 8.3 of the protocol.

All AESI will be presented in a listing

## 9.2 Clinical Laboratory Evaluations

All clinical laboratory summaries will be based on central laboratory data using the conventional units provided by the central laboratory. However, in listings results with both conventional and standard units will be provided.

Descriptive statistics for central laboratory safety parameters including absolute values and change from baseline values will be summarised with n, mean, SD, median, minimum and maximum values by treatment regime and by respective visits and timepoint if applicable.

Analysis of potentially clinically significant abnormality (PCSA) will be performed based on the PCSA criteria. For parameters for which no PCSA criteria are defined, similar analyses will be done using the normal range, if applicable. Analyses according to PCSA will be performed based on the worst value during the treatment emergent period, using all measurements (either local or central, either scheduled, nonscheduled or repeated).

For laboratory variables, vital signs and ECG variables, the incidence of patients with at least one PCSA during the treatment-emergent period including unscheduled, early termination or safety follow-up visits will be summarized regardless of the baseline level and according to the following baseline status categories:

- Normal/missing
- Abnormal according to PCSA criterion or criteria;

Changes in central laboratory data will also be summarized using shift tables from baseline to the worst toxicity grade.

Laboratory data collected at all visits including unscheduled, early termination or safety follow-up visits will be included in listings and will contribute to tables of shifts from baseline and in tables showing change from baseline grade to the worst toxicity grade. Unscheduled laboratory results will not be windowed for the purposes of assigning a nominal visit.

All vital sign, physical examination and ECG data including unscheduled, early termination or safety follow-up visits are mapped to analysis visits and are included in the summary.

### 9.2.1. Haematology

The following laboratory tests will be included in haematology summary tables: WBCC and differentials, RBCC, RDW, Hb, HCT, nucleated red blood cells, platelet count, MCH, MCHC, MCV and MPV. All hematology data will be presented by patient in a listing.

### 9.2.2. Serum Chemistry

The following laboratory tests will be included in clinical chemistry summary tables : albumin, sodium, potassium, chloride, bicarbonate, urea, creatinine, glucose, calcium, phosphate, ALT, AST, GGT, LDH, alkaline phosphatase, total protein, iron, total bilirubin and CPK. All chemistry data by patient will be presented in a listing.

### 9.2.3 Urinalysis

The following urinalysis laboratory tests will be included in summary tables: pH, protein, glucose, ketones and blood. All data by patient will be presented in a listing.

### 9.3. Vital Sign Measurements

Vital signs parameters include systolic blood pressure (mmHg), diastolic blood pressure (mmHg), temperature (°C/F), and heart rate (beats/min). Summary tables by treatment group presenting observed values and changes from baseline at each scheduled post-baseline visit will be presented for vital signs by treatment group and overall. Change from baseline will only be calculated for patients having non-missing baseline and post-baseline measurements.

The incidence of PCSA in vital sign will be summarized using counts and percentages of patients by treatment groups and also will be summarized using shift tables from baseline to follow-up visits.

All vital sign data by patient will be presented in a listing. PCSA criteria will be flagged in the listing.

### 9.4. Physical Examination

A table will summarize physical examination results presenting counts and percentages by treatment group and overall. The incidence of clinically significant changes in physical examinations will be summarized using counts and percentages of patients with the body system as normal, abnormal not clinically significant or abnormal clinically significant. Physical examination results for all patients will be presented in a listing.

### 9.5. 12-lead ECG

12-lead ECG parameters include normal sinus rhythm, ventricular rate (beats/min), PR interval (msec), QRS duration (msec), QT interval (msec), QTcF interval (msec) and QTcB interval (msec). The QTcB and QTcF will be derived using the following formula:

**Bazett Formula:**  $QTc = QT \text{ interval} / \sqrt{(RR \text{ interval})}$

**Fridericia Formula:**  $QTc = QT \text{ interval} / (RR \text{ interval})^{1/3}$

RR interval = 60/ventricular rate

Absolute values and change from baseline to each scheduled post-baseline visit in ECG continuous variables will be summarized with n, mean, SD, standard error of the mean (SEM), median, minimum and maximum values by treatment group and overall. Change from baseline will only be calculated for patients having non-missing baseline and post-baseline measurements.

The number (n) and percentage (%) of patients with treatment-emergent PCSA will be summarized by different treatment groups using count and percentages of patients.

Changes in ECG data will also be summarized using shift tables .

Data listings by patient will be provided. PCSA criteria will be flagged in the listing.

## 9.6. Local Skin Reactions

Descriptive statistics (for diameter of erythema and induration will be provided overall and by treatment group. The counts and percentages of patients with pain, itchiness, and tenderness will be provided. All injection site reaction data by patient will be presented in a listing

## 9.7. Virology

Positive samples for HIV, HBsAg, HBcAb, [REDACTED] and hepatitis C at the Screening Visit will be listed by patient.

## 9.8. Other Analysis

The impact of the COVID-19 will be summarized by study treatment group and overall. The table will present the counts and percentages of patients for the following categories:

- Number (%) of Patients with COVID-19 up to Baseline (Week 0)
- Number (%) of Patients with COVID-19 from Baseline (Week 0) up to Week 24
- Number (%) of Patients with COVID-19 from Week 24 up to Week 68
- Number (%) of Patients with COVID-19 from Baseline (Week 0) to Week 68
- Number (%) of Patients with COVID-19 leading to study discontinuation from Baseline (Week 0) up to Week 24
- Number (%) of Patients with COVID-19 leading to study discontinuation from Week 24 up to Week 68
- Number (%) of Patients with COVID-19 leading to study discontinuation from Baseline (Week 0) to Week 68

- Number (%) of Patients with COVID-19 leading to study drug discontinuation from Baseline (Week 0) up to Week 24
- Number (%) of Patients with COVID-19 leading to study drug discontinuation from Week 24 up to Week 68
- Number (%) of Patients with COVID-19 leading to study drug discontinuation from Baseline (Week 0) to Week 68

All COVID-19 infection data by patient will be presented in a listing. A Separate listing will be prepared for listing COVID-19 infection data leading to study discontinuation, leading to study drug discontinuation.

## 10. Pharmacokinetics

All PK listings and individual concentration-time profiles will be presented using the SAF set. PK tables, mean figures and all statistical analyses will be presented using the PK set.

Population pharmacokinetic analysis will be to be conducted per separate analysis plan and reported separately.

### 10.1. Data Handling

Serum concentrations that are below the limit of quantification (BLQ) will be treated as zero for calculation of concentration descriptive statistics.

### 10.2. Serum Concentrations

Blood samples will be collected at the following time points for PK assessment:

Predose (Day 1), Day 8, Day 15, Day 29, Day 57, Day 85, Day 113, Day 120, Day 141, Day 169, Day 176, Day 197, Day 225, Day 253, Day 281, Day 309, Day 337, and Day 365.

PK collections that have an actual sampling time that deviates from the predefined collection time window ( $\pm 3$  days) or that are collected post-dose (except at Day 8, Day 15, Day 120 and D176) will be flagged in the data listings and excluded from the calculation of concentration summary statistics. In addition, when patients withdraw from the treatment earlier and still have PC collection at one or more later visits, the pre-dose PC data collected from 25 to 31 days post last dose (ie, corresponding to the time window of the next scheduled administration) are still included in the analysis.

Individual serum concentrations will be expressed in  $\mu\text{g/mL}$  and will be presented in data listings and summarized separately using descriptive statistics (number of observations, arithmetic mean, SD, CV%, median, minimum, and maximum) by treatment group and visit weeks. Serum concentration summaries will also be presented by ADA status (e.g. ADA positive, ADA negative), where data permit.

Individual serum concentrations will be plotted by actual time on linear scale. Mean serum concentrations will be plotted by treatment and visit weeks on linear scale with all dose levels overlaid on the same plots. Mean serum concentration plots will also be presented by ADA status (e.g. ADA positive, ADA negative), where data permit.

Serum concentrations will be reported to 3 significant figures in summary statistics except CV%, which will be reported to 1 decimal place.

### 10.3. Immunogenicity

All the analysis will be performed using Anti-drug Antibody Sets.

Patient's ADA status, response variable and kinetics of ADA responses (see definitions below) will be summarized on the ADA population.

Kinetics of ADA responses will be described for patients with treatment-induced ADA and for patients with treatment-boostered ADA, separately. Time to ADA onset and duration of ADA will be described with minimum, Q1, median, Q3 and maximum statistics.

Peak titer will be described with minimum, Q1, median, Q3 and maximum statistics for patients with treatment-induced ADA and for patients with treatment-boostered ADA, separately.

Sample status (negative, positive, inconclusive) will be described using descriptive statistics.

The impact of positive immune response on efficacy, PK and safety variables may be further explored, depending on ADA incidence.

#### Patient's ADA status

- Patients with **pre-existing ADAs** correspond to patients with ADAs present in samples drawn before first administration of intervention. Patients with missing ADA sample at baseline will be considered as without pre-existing ADA.
- Patients with **treatment-emergent ADA** correspond to patients with at least one treatment-induced/boostered ADA.
- Patients with **treatment-induced ADAs** correspond to patients with ADAs that developed during the treatment-emergent (TE) period and without pre-existing ADA (including patients without pre-treatment samples).
- Patients with **treatment-boostered ADAs** correspond to patients with pre-existing ADAs that are boosted during the TE period to a significant higher titer than the baseline. A 2-fold serial dilution schema is used during titration, so at least a 4-fold increase will be considered as significant.
- Patients with **unclassified ADA** correspond to patients with pre-existing ADAs that cannot be classified as treatment-boostered ADA because of missing titer(s) (ie, a positive ADA sample during the TE period in a patient with pre-existing ADA but with missing titer at this sample or at baseline).

- Patients **without treatment-emergent ADA** correspond to patients without treatment-induced/boosted ADA and without any inconclusive sample nor unclassified ADA during the TE period.
- Patients **with inconclusive ADA** are defined as patients which cannot irrefutably be classified as with or without treatment-emergent ADA.

### **Kinetics of ADA response**

Kinetics of ADA response will be derived for patients with treatment-induced/boosted ADA considering ADA samples collected during the TE period and post-treatment period.

- Time to onset of ADA response is defined as the time period between the first IMP administration and the first treatment-induced/boosted ADA.
- Duration of ADA response is defined as the time between the first treatment-induced/boosted ADA and the last treatment-induced/boosted ADA, irrespective of negative samples or positive samples not reaching the boosted threshold in-between. ADA duration will be summarized only for patients with persistent ADA response.
- Persistent ADA response is defined by treatment-induced/boosted ADA with a duration of ADA response of at least 16 weeks.
- Transient ADA response is defined by treatment-induced/boosted ADA with a duration of ADA response of less than 16 weeks and the last sample of the TE period is not treatment-induced/boosted.
- Indeterminate ADA response is defined by treatment-induced/boosted ADA that are neither persistent nor transient.

### **ADA response variable:**

- ADA incidence is defined as the proportion of patients found to have seroconverted (treatment-induced ADAs) or boosted their pre-existing ADA response (treatment-boosted ADAs) at any time point during the TE period.

#### **10.4. Serum Pharmacokinetic Parameters**

Not applicable.

#### **10.5. Pharmacokinetic Statistical Analysis**

Not applicable.

## **12. Interim Analysis**

An interim analysis will be performed when approximately ■ patients in each arm complete the Week 16 assessments accounting for “no dropouts”.

The IA data cut-off date will be defined as the date when approximately [REDACTED] participants in each of the 5 treatment arms (500 mg loading dose + 250 mg Q4W, 250 mg Q4W, 125 mg Q4W, 62.5 mg Q4W and Placebo Q4W) have completed 16 weeks of treatment in the study.

For Interim Analysis, the interim analysis subject list will be based on the analysis population consisting of 2 sets of patients: (1) the randomized patients who complete the Week 16 visit; (2) the randomized patients who discontinue study before Week 16, but were randomized in the study early enough that the patients could have completed Week 16 visit by IA data cut-off date if not early discontinued. [REDACTED]

The below analysis sets will only be used for the Interim Analysis and will contain subjects from the respective analysis sets defined in Section 4.3 who are also in the interim analysis subject list:

- IA-Full Analysis Set for Part 1
- IA-Full Analysis Set for Part 2
- IA-Pharmacokinetic Set for Part 1
- IA-Pharmacokinetic Set for Part 2
- IA-Anti-drug Antibody Set for Part 1
- IA-Anti-drug Antibody Set for Part 2

The above analysis sets will be used for summaries of demographics and baseline characteristics, medical history, rescue medication and prior/concomitant medications and procedures, efficacy analyses, pharmacokinetics and immunogenicity. For the other analyses, the patients included in the analysis will correspond to the already defined analysis set, such as SAF1, SAF2, etc by the date of interim analysis data cut-off. For disposition, all patients enrolled by IA data cut-off date will be summarized.

[figure not shown]
For the interim analysis, the below parameters will be evaluated:

- Disposition of Patients
- Demographics and Baseline Characteristics
- Disease-Specific History, Medical history
- Prior & Concomitant Medications and procedures
- Rescue Medication
- Efficacy parameters, e.g. including but not limited to EASI, IGA, NRS etc
- Drug exposure
- Adverse events
- Laboratory values, ECG, Vital signs, Physical examination, Local Skin Reactions, [REDACTED]
- Pharmacokinetics
- Immunogenicity

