3.5 Early Study Termination

The study can be terminated at any time for any reason by the Sponsor (including approval or the favourable opinion is revoked, in the event of a negative change in the benefit/risk ratio when the necessary adjustment to the maximum sum insured is not possible; failure to enrol; futility; safety decision etc). If the trial is suspended or terminated early, the Investigator will promptly inform the trial patients and should assure appropriate therapy and follow-up.

No further IMP will be given to a patient if any study permanent discontinuation rules are met (see Section 9.1), including recommendation of the Independent Data Monitoring Committee (IDMC; Section 3.8). If a patient withdraws from the study treatment early but consent is retained, study assessments may be continued until a) Day 169 (Week 24) for patients who withdraw from study treatment during the first study period and therefore are **not** eligible for

Version number: 1

1-Mar-2022

LTE, or b) until Day 365 (Week 52) or the end of the safety follow-up period in patients who withdraw from study treatment after Day 169 (Week 24).

Unless patients continue in the LTE at Day 169 (Week 24) or due to loss of clinical response at or after Day 197 (Week 28), a safety follow-up for 140 days after the last dose of IMP will be required.

In addition, the Investigator may withhold further IMP from a patient if they report moderate-or-severe (regardless of seriousness) adverse reactions which are attributed to the IMP. There will be no obligation to unblind treatment allocation in making this decision.

The Sponsor may discontinue the entire study at any time based on information received during the running of the study that demonstrates an unexpected risk or absence of benefit to patients. This may for example follow the request of the IDMC or where additional information emerges either during the study or from other sources (eg, literature or Health Authorities).

If the study is discontinued, where patients withdraw early or where IMP has been discontinued by the Investigator, patients will be required to be followed-up for a minimum of 140 days for safety evaluation.

Further details of IMP discontinuation are provided in Section 9.1.

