9.1.3 Follow-up of Patients Off Treatment

If a patient discontinues study treatment prematurely, she/he will be encouraged to remain in the study to complete all remaining study visits and to participate in all assessments according to the Schedule of Assessments. Their study data collected during their continued involvement is important to the study efficacy analysis and study value.

If a patient permanently withdraws from study treatment early but consent is retained, study assessments may be continued until Day 169 (Week 24) for patients who withdraw from study treatment in the first study period (and who are therefore no longer eligible for consideration for the LTE at Day 169 (Week 24) or progression to the next study period), or until Day 365 (Week 52) in patients who withdraw from study treatment after Day 169 (Week 24) and who decide not to participate in or are **not** eligible for the LTE study. This may be followed by the safety follow-up according to the Schedule of Assessments (Section 6.1).

If a patient chooses not to attend remaining visits in the event of withdrawal from study treatment early before Day 169 (Week 24) or Day 365 (Week 52), they will instead enter the safety follow-up and complete their assessments as per the Schedule of Assessments (Section 6.1).

Patients will be considered lost to follow-up only if no contact has been established by the time the study is completed, such that there is insufficient information to determine the patient's status at that time. Patients who refuse to continue participation in the study, including telephone contact, should be documented as "withdrawal of consent" rather than "lost to follow-up." Investigators should document attempts to re-establish contact with missing patients throughout the study period. If contact with a missing patient is re-established, the patient should not be considered lost to follow-up, and evaluations should resume according to the protocol.

The following actions must be taken if a patient fails to return to the clinic for a required study visit:

• The site must attempt to contact the patient and reschedule the missed visit as soon as possible and counsel the patient on the importance of maintaining the assigned visit schedule.

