#### 4.3.1. All Enrolled Set

All Enrolled Analysis Set includes all patients who signed an informed consent form with no screen failures. Analysis will be based on treatment allocated at randomisation.

#### 4.3.2. Full Analysis Set for Part 1

The Full Analysis Set (FAS1) for Part 1 includes all randomised patients up to week 24. Efficacy analysis will be based on treatment allocated at randomisation.

#### 4.3.3. Full Analysis Set for Part 2

The Full Analysis Set (FAS2) for Part 2 includes all re-randomised patients at Week 24 up to week 52. Efficacy analysis will be based on treatment allocated at re-randomisation.

#### 4.3.4. Safety Analysis Set for Part 1

The safety set (SAF1) for Part 1 will consist of all patients who take at least one dose of study treatment, including Placebo up to week 24. Any analysis based on the SAF1 will be based on the treatment actually received, regardless of assigned treatment according to the planned randomisation.

#### 4.3.5. Safety Analysis Set for Part 2

The safety set (SAF2) for Part 2 will consist of all re-randomised patients at Week 24 who take at least one dose of study treatment on or after Week 24. Any analysis based on the SAF2 will be based on the treatment actually received at week 24, regardless of assigned treatment according to the planned randomisation.

#### 4.3.6. Pharmacokinetic Set for Part 1

The PK set will consist of all randomized patients in the SAF1 with at least one post-Baseline PK sample (with adequate documentation of dosing and sampling dates and times) up to week 24. Any analysis based on the PK1 will be based on the treatment actually received, regardless of assigned

treatment according to the planned randomisation. Patients who received only placebo will not be included.

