## 5. Patient Disposition

### 5.1 Disposition

Patient disposition will be summarized by study treatment group and overall.

Disposition of patients includes the counts and percentages of patients for the following categories: screened, screen failures, randomized, patients who completed the study treatment, patients who discontinued from the study treatment, patients who completed the study, patients who discontinued from the study, patients who completed Week 24, patients re-randomised at Week 24, number of patients who enter in LTE, patients who discontinued from study treatment prior to Week 24, patients who discontinued from study prior to Week 24, and patients who provide consent for the skin biopsy sub-study. For patients who discontinue treatment prior to week 24 or discontinue study prior week 24, the denominator will be the number of patients randomized for part 1. For screened and screen failure, only the total count will be provided.

Similar disposition items will be summarized for Part 2, treatment completion, early discontinuation from treatment, study completion, early discontinuation from study, etc. The denominator for Part 2 disposition table will be the number of patients that were re-randomized at Week 24.

The primary reasons for study and treatment discontinuation will be also provided.

Study analysis population will be summarized for Part 1 by Part 1 randomization arms; for Part 2 by Week 24 re-randomization treatment arms.

Any discontinuation due to COVID-19 will also be summarized.

Patient disposition and discontinuation data will be presented in a listing.

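### On its visible wording, the interim efficacy population omits patients who stop drug and enter safety follow-up, and on-study patients with no Week 16 visit, so interim response rates can be overstated

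*SAP*

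**What the plan says.** SAP section 12 states that "the interim analysis subject list will be based on the analysis population consisting of 2 sets of patients". The first is "1) the randomized patients who complete the Week 16 visit". The second is "2) the randomized patients who discontinue study before Week 16, but were randomized in the study early enough" to have completed that visit by the cut-off had they stayed. The interim full analysis, PK and ADA sets keep only members of the section 4.3 sets "who are also in the interim analysis subject list", and the interim efficacy analyses use them. A redacted run follows the definition directly.

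Three other places bear on this:

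- SAP section 5.1 counts "patients who discontinued from study treatment prior to Week 24, patients who discontinued from study prior to Week 24" as separate disposition items.
- Protocol section 9.1.3 says of patients who stop treatment early and choose not to attend the remaining visits that "they will instead enter the safety follow-up and complete their assessments as per the Schedule of Assessments". Protocol section 3.5 adds that, apart from patients who move to the LTE, "a safety follow-up for 140 days after the last dose of IMP will be required".
- The Part 1 full analysis set in SAP section 4.3.2 "includes all randomised patients up to week 24", with no condition on visit or treatment status.

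**The concern.** The early-enough condition in the second group shows the intent: the interim should cover everyone with the opportunity to reach Week 16, whether or not they did. As worded, the rule selects on what happened to the patient. Someone with the same randomisation date is in if they attend Week 16, in if they leave the study before it, and out if they stop drug and remain in follow-up or simply miss the visit.

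The omitted patients are unlikely to be a random sample. Protocol section 5.3.4 makes several kinds of rescue use a reason for stopping IMP, so early stoppers probably include many poor responders. Section 9.1.3 adds that they lose eligibility for the LTE at Day 169, which removes one reason to keep attending. According to Protocol section 3.3, the interim serves phase 3 planning and looks at percentage change in EASI and EASI 75 at Week 16. Those are the estimates exposed.

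**Working it through.** **1. Does follow-up keep a patient on study past Week 16?** Week 16 is Day 113. Planned doses before it fall on Days 1, 29, 57 and 85. Planned end of safety follow-up = last dose day + 140:

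- Day 1 + 140 = Day 141
- Day 29 + 140 = Day 169
- Day 57 + 140 = Day 197
- Day 85 + 140 = Day 225

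All are later than Day 113. A patient on this path who has declined the Week 16 visit has not completed it and, unless they also leave follow-up early, has not left the study before it. The cut-off date does not change this: finishing follow-up on Day 197 is still not leaving before Week 16. An on-study patient with no Week 16 visit fails both conditions directly.

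**2. What do the documents say about numbers?** Protocol section 3.6 assumes 30% dropout to Week 24, and its figure reproduces: 70 × (1 − 0.30) = 49 completers per arm. Section 1.5.3 cites about 20% dropout without a time point. Neither figure is the omitted share. Patients who leave the study before Week 16 are retained by the second group, and those who stop drug but attend Week 16 are in the first. The share f must therefore be assumed.

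**3. Size of the effect on a response rate.** Let p be the rate among all patients with the opportunity to reach Week 16, f the omitted share and q the rate among those omitted. Then

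reported rate = (p − f·q)/(1 − f), which is p/(1 − f) when q = 0.

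For illustration, p is taken from the phase 2a EASI 75 results in Protocol Table 1-1: 51.9% (high dose) and 25.0% (placebo). With q = 0:

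| f (assumed) | 51.9% becomes | 25.0% becomes |
|---|---|---|
| 2% | 53.0% | 25.5% |
| 5% | 51.9/0.95 = 54.6% | 25.0/0.95 = 26.3% |
| 10% | 51.9/0.90 = 57.7% | 25.0/0.90 = 27.8% |
| 20% | 64.9% | 31.25% |

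**4. Dependence on q.** At f = 10% and p = 51.9%:

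- q = 25%: (51.9 − 2.5)/0.90 = 54.9%, an excess of 3.0 points instead of 5.8
- q = 51.9%: no bias
- q = 60%: (51.9 − 6.0)/0.90 = 51.0%, an understatement

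**5. Difference from placebo.** The true difference is 51.9 − 25.0 = 26.9 points. With q = 0:

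- f = 10% in both arms: 26.9/0.90 = 29.9
- f = 10% active, 5% placebo: 31.4
- f = 5% active, 10% placebo: 26.9 (essentially unchanged)
- f = 5% active, 15% placebo: 25.2

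**The case against.** The strongest reply is that the wording cannot be judged complete. Redacted text sits directly after the definition, where a further rule on the list would naturally go, and the estimand and intercurrent-event tables are not visible. That stands: the point is conditional on the redacted text, and counting omitted patients as non-responders is an assumption.

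The gap is also narrower than it first looks. Protocol section 5.3.4 and SAP section 7.4 ask all patients to keep attending whether or not they complete treatment or use rescue, and Protocol section 9.1.3 encourages the same. The SAP's efficacy windows map scheduled or unscheduled assessments on Days 100 to 127 to Week 16, which may recover some late visits. The omitted share could be small.

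The consequence is limited too. Protocol section 3.3 says the interim will not change study conduct. Interim disposition covers all patients enrolled by the cut-off, and safety summaries use the ordinary safety sets, so these patients are not hidden from interim readers. The primary analysis uses all randomised patients.

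A reader might infer that interim rates are overstated in every arm and the treatment effect with them. The documents do not support that. It would require every arm to have omitted patients who respond less often than those included, and nothing visible establishes this. If placebo patients are omitted more often, the difference can shrink.

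**Conclusion.** The gap holds on the visible wording. Two identifiable groups of randomised patients, both with the opportunity to reach Week 16, are left out of the interim full analysis set because list membership depends on visit completion or study discontinuation. This departs from the evident intent of the rule and from the all-randomised set used in the final analysis.

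Overstatement of interim response rates is plausible, not shown. On the illustrative 51.9%, it would be about 2.7 points at f = 5% and 5.8 points at f = 10%, if all omitted patients are non-responders. It shrinks as their response rate rises and vanishes when that equals the overall rate. No direction can be given for the difference from placebo. This is a modest point about estimates used for phase 3 planning. It does not touch trial conduct or the final Part 1 analysis.

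**What to change.** In SAP section 12, keep the first group and replace the second with: *every other randomised patient whose randomisation date left time to reach the Week 16 visit before the cut-off, irrespective of whether the patient missed that visit, stopped IMP, moved to safety follow-up or left the study.* State that their missing Week 16 data follow the final-analysis estimand rules.

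Keeping the first group matters. A fixed requirement of 113 or 116 days since randomisation, used alone, would remove some valid completers: Day 113 is only 112 days after Day 1, and the ±3-day window allows the visit on Day 110.

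If the redacted text already covers these patients, confirmation is enough. The cost is one sentence and a few more patients with missing data under rules the SAP already provides. Interim rates may look slightly less favourable.
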